9.3 CTCAE Routine Reporting Requirements

In addition to the solicited adverse events listed in Section 9.1, the following table outlines the combinations of time points, grades and attributions of AEs that require routine reporting to the Alliance Statistics and Data Center. Attribution refers to radiation and reconstruction. Adverse events attributed to chemotherapy need not be reported. Questions about routine reporting should be directed to the Data Manager.

*Combinations of CTCAE Grade & Attribution Required for Routine AE Data Submission on Case Report Forms (CRFs)

Attribution	Grade 1	Grade 2	Grade 3	Grade 4	Grade 5
Unrelated			a	a	a
Unlikely			a	a	a
Possible	a	a	a, b	a, b	a, b
Probable	a	a	a, b	a, b	a, b
Definite	a	a	a, b	a, b	a, b

- a) Adverse Events: Other CRF - Applies to AEs occurring between registration and within 30 days of the patient's last treatment date, or as part of the Clinical Follow-Up Phase.
- b) Adverse Events: Late CRF - Applies to AEs occurring greater than 30 days after the patient's last treatment date.

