9.1 Routine Adverse Event Reporting

Adverse event data collection and reporting, which are required as part of every clinical trial are done to ensure the safety of patients enrolled in the studies as well as those who will enroll in future studies using similar agents. Adverse events are reported in a routine manner at scheduled times according to the study calendar in Section 5.0. For this trial, Solicited Adverse Event Solicited form is used for routine AE reporting in Rave.

Acute Adverse Events: Acute adverse events, will be scored per CTCAE 4.0 regardless of attribution. Attribution will however be collected for separate analysis.

Late Radiation Adverse Events: Late radiation complications will be defined as those that are present ≥ 6 months after the final dose of radiation and include CTCAE 4.0 grade 3+:

9.2 Solicited Adverse Events:

The following adverse events are considered "expected" and their presence/absence should be solicited, and severity graded, at baseline and for each cycle of treatment.

9.2.1 Radiation Therapy Complications:

CTCAE v4.0 Term	CTCAE v4.0 System Organ Class (SOC)
Fibrosis, deep connective tissue	Musculoskeletal and connective tissue disorders
Superficial soft tissue fibrosis	Musculoskeletal and connective tissue disorders
Chest wall pain	Musculoskeletal and connective tissue disorders
Joint range of motion decreased	Musculoskeletal and connective tissue disorders
Wound Infection	Infections and infestations
Fatigue	General disorders and administration site conditions
Dermatitis radiation	Injury, poisoning and procedural complications
Wound complication	Injury, poisoning and procedural complications
Wound dehiscence	Injury, poisoning and procedural complications
Lymphedema	Vascular disorders
Telangiectasia	Skin and subcutaneous tissue disorders
Hypothyroidism	Endocrine Disorders
Myocardial Infarction	Cardiac disorders
Cardiac disorders – Other specify*	Cardiac disorders
Pulmonary fibrosis	Respiratory, thoracic and mediastinal disorders
Brachial Plexopathy	Nervous system disorders
Peripheral motor neuropathy	Nervous system disorders
Peripheral sensory neuropathy	Nervous system disorders
Treatment related secondary malignancy	Neoplasms benign, malignant and unspecified (including cysts and polyps)

* Specific cardiac events, if and when they occur will be recorded on the Adverse Events: Other form.

9.2.2 Non CTCAE RT Associated Complications:

- a) Shoulder stiffness (occasional) (Grade 1-3)

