10.2 Acute and Late Radiation Complications

Acute Adverse Events: Acute adverse events, will be scored per CTCAE 4.0 regardless of attribution. Attribution will however be collected for separate analysis.

Late Radiation Adverse Events: Late radiation complications will be defined as those that are present ≥ 6 months after the final dose of radiation and include CTCAE 4.0 grade 3+:

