12.0 STATISTICAL CONSIDERATIONS

12.1 Study Design

This is a randomized, two-arm, un-blinded, non-inferiority trial comparing the impact of hypofractionated dosing (vs. standard dosing) of radiation on the 24-month breast reconstruction complication rate.

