12.4 Supplementary/Secondary Analysis Plans

12.4.1 Secondary Objectives

Incidence of acute and late radiation complications based on CTCAE 4.0 toxicity. The proportion of patients with acute or late radiation complications, will be estimated separately by treatment arm and will be compared across the two arms using two-sample test of proportions (Z test) with a two-sided alternative.

Local and local regional recurrence rate: The cumulative incidence of local and local regional recurrence will be estimated separately by treatment arm using the cumulative incidence function treating death as the competing risk and will be compared using Gray's test. In addition, local and local regional recurrence free survival will be summarized for each arm using the Kaplan-Meier estimators, and will be compared using a log rank test.

Reconstruction complication rates based on reconstruction method (autologous +/- implant vs. implant only) and timing of reconstruction received (immediate vs. intent for delayed): Between-arm differences in reconstruction complication rates will be assessed separately within each of the six subgroups based on type and timing of reconstruction. Between-arm differences in complication rates will also be assessed within the two broader subgroups of patients who receive implant only and those who receive autologous based reconstruction. Within each subgroup, the comparison will be done using a two-sample Z test of proportions with a two-sided alternative as described for the primary analysis in Section 12.3.2.

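### Section 9.3 excuses events attributed to chemotherapy although acute events are to be scored whatever their attribution; the clear exposure is events entered on the Other form, not the whole acute comparison

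*Combined protocol and SAP*

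**What the plan says.** Section 9.1 sets the rule for acute toxicity: "Acute adverse events, will be scored per CTCAE 4.0 regardless of attribution". Section 10.2 repeats it and adds: "Attribution will however be collected for separate analysis". Attribution is thus meant to be a variable for analysis, not a filter on what is collected.

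Section 9.2 covers the solicited events. For these, "their presence/absence should be solicited, and severity graded, at baseline and for each cycle of treatment". Section 9.2.1 lists 19 CTCAE terms under a heading for radiation therapy complications, and no attribution condition is attached. A footnote sends specific cardiac events to the Adverse Events: Other form.

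Section 9.3 opens: "In addition to the solicited adverse events listed in Section 9.1, the following table outlines" the combinations of time, grade and attribution that need routine reporting. It then defines its terms, "Attribution refers to radiation and reconstruction", and follows with the exemption: "Adverse events attributed to chemotherapy need not be reported". The table requires grade 3-5 events rated Unrelated or Unlikely on the Other form. It does not require grade 1-2 events with those ratings. The exemption sentence appears again in the list of exclusions from expedited reporting in 9.4.1.

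For the analysis, 12.4.1 says: "The proportion of patients with acute or late radiation complications, will be estimated separately by treatment arm", with a two-sided two-sample Z test between arms. It does not say which terms, grades, time window or forms make up an acute radiation complication. Section 12.1 describes the design: "This is a randomized, two-arm, un-blinded, non-inferiority trial".

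**The concern.** The exemption carries no limit by term, grade, form or visit. A site reading 9.3 alone may leave out an acute event that 9.1 and 10.2 say must be scored. The person who decides whether the event belongs to chemotherapy, and so whether it enters the data, knows the treatment arm.

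An event that is never entered cannot be recovered by analysis. If omission is equal in the arms, acute incidence is understated. If it differs, the between-arm comparison in 12.4.1 is biased as well.

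Unequal omission needs no bad faith. Arm 1 lasts 5-6 weeks and Arm 2 lasts 3-4, and the calendar times visits from radiation. For a patient who had chemotherapy first, with the same gap before radiation, the end-of-radiation visit falls about two weeks nearer the last cycle in Arm 2. Chemotherapy is then a somewhat more plausible explanation in that arm.

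**Working it through.** The plan states no figure on this point, so the main check is to set the rules side by side.

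1. **Exemption against the scoring rule.** Take an acute event that the investigator attributes to chemotherapy. Under 9.1 and 10.2 it is scored. Under 9.3 it may be left out. Both cannot hold.

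2. **Exemption against the table.** In 9.3, attribution means radiation and reconstruction, so an event due to chemotherapy falls in the Unrelated or Unlikely rows. At grade 3-5 those rows require it, and the sentence beside the table excuses it.

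3. **What the framing protects.** Section 9.3 is additional to the solicited events, although it locates them in Section 9.1 when the list is in 9.2. Read in that light, solicited terms are graded whatever their cause. The exemption sentence itself does not say so.

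4. **What the framing does not protect.** Specific cardiac events go to the Other form, which is form (a) of the 9.3 table. Pneumonitis is not among the 19 solicited terms (only pulmonary fibrosis is). Section 9.4.1 sends it to routine reporting, so it enters through 9.3. Other unsolicited acute events do the same.

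5. **Chemotherapy exposure.** Section 7.3 bars cytotoxic therapy during radiation and requires at least 21 days on either side. What remains is carry-over from earlier chemotherapy, and chemotherapy begun 21 days or more after radiation, which can overlap the 2-8 week visit.

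**Illustration (assumed rates).** Inputs: n = 396 evaluable patients per arm (12.2); the same true acute rate p in both arms, assumed 10% to 40%; and f1, f2, the assumed share of patients with an acute event who drop out of the count in Arms 1 and 2.

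- Observed rates: p1 = p(1 - f1), p2 = p(1 - f2). False difference: D = p1 - p2 = p(f2 - f1).
- With m = (p1 + p2)/2: s0 = sqrt[2m(1 - m)/n] and s1 = sqrt[(p1(1 - p1) + p2(1 - p2))/n].
- Rejection rate = 1 - Φ[(1.96 s0 - D)/s1] + Φ[(-1.96 s0 - D)/s1].

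Worked case, p = 40%, f1 = 5%, f2 = 20%: p1 = 0.38, p2 = 0.32, D = 0.06, m = 0.35, s0 = 0.0339, s1 = 0.0338. Then (1.96 × 0.0339 - 0.06)/0.0338 is about 0.19, and the rejection rate is 42.5%.

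| True rate | Omitted, Arm 1 / Arm 2 | Observed | False difference | Rejection rate |
|---|---|---|---|---|
| 10% | 10% / 10% | 9.0% / 9.0% | 0 | 5.0% |
| 40% | 10% / 10% | 36.0% / 36.0% | 0 | 5.0% |
| 10% | 5% / 10% | 9.5% / 9.0% | 0.5 points | 5.7% |
| 40% | 5% / 10% | 38.0% / 36.0% | 2.0 points | 9.0% |
| 10% | 5% / 20% | 9.5% / 8.0% | 1.5 points | 11.6% |
| 40% | 5% / 20% | 38.0% / 32.0% | 6.0 points | 42.5% |

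When the true rates are equal, a false difference therefore requires omission that differs by arm.

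**The case against.** **Most of the acute data are protected.** A reader might infer that the acute comparison as a whole rests on open-label attribution. The documents do not support that. The main acute radiation terms are solicited and graded with no attribution condition, and the solicited form is the routine reporting form. Nor do they support the inference that baseline grades left by earlier chemotherapy would be lost, since 9.2 asks for grading at baseline. This objection stands and sets the scope of the point. What survives is the Other-form events and the risk that a site applies an unlimited sentence too widely.

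**The endpoint may be the solicited list.** The 9.2.1 heading makes that a natural reading of 12.4.1, and unsolicited events would then not enter the test. But 12.4.1 does not say so, and specific cardiac events are both solicited and entered on the Other form. The calendar's record review of cardiac events starts only at 6 months, when events count as late.

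**The sentence may be a deliberate exception to the table.** That reading is coherent, and deaths are in any case reported whatever the cause (9.4). It does not reconcile the sentence with 9.1 and 10.2.

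**The size is assumed.** A reader might take the share of patients with an event that could be blamed on chemotherapy (say 10-40%) times the between-arm gap in blame (say 10-20 points) and infer a bias of 1 to 8 points. Neither input is in the documents. The product is also an upper bound for a patient-level proportion, because a patient whose fatigue is omitted still counts if she has another qualifying event such as radiation dermatitis. This objection stands.

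**Open-label grading remains.** Unblinded staff grade every event whatever 9.3 says. Correcting 9.3 closes one route of omission and does not remove that bias.

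**Conclusion.** The concern holds in limited form. The 9.3 exemption cannot be followed together with the acute scoring rule in 9.1 and 10.2, and at face value it also conflicts with the grade 3-5 rows of its own table. The clear exposure is to specific cardiac events, pneumonitis and other unsolicited acute events on the Other form. A further exposure, dependent on site behaviour, is to solicited terms such as fatigue or neuropathy.

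The size is unknown. The tabulated rates show only how the test would behave under assumed omission and are not estimates for this trial. A claim of bias between arms needs the further assumption that omission differs by arm.

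The consequence is confined to secondary objective 2.2.1. A reader might infer a threat to the non-inferiority conclusion, but 9.2.3 records reconstruction complications separately from CTCAE toxicity and the decision rules in 12.3.2 do not use acute toxicity. This is a cheap improvement worth making, not a flaw in the main result.

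**What to change.** **Section 9.3.** Delete the exemption, or limit it so that it does not apply to:

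- the solicited terms in 9.2.1 and 9.2.2 at any visit, including specific cardiac events on the Other form;
- pneumonitis;
- the grade 3-5 events that the table requires.

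Record chemotherapy as an attribution field instead. Correct the pointer to the solicited list from 9.1 to 9.2, and state that the repeated sentence in 9.4.1 concerns expedited reports only.

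**Section 12.4.1.** Define acute radiation complications by term, grade, time window and form. Make the main comparison the one scored regardless of attribution, on the solicited terms plus pneumonitis. Keep the radiation-attributed analysis as supportive, which is the separate analysis that 9.1 and 10.2 already promise.

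**Cost.** A few sentences, a memo to sites, one attribution field and a few more grade 3-5 entries. The solicited terms are already on the form. The change has to be made at data collection, because events left out cannot be restored later.

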9.4 Expedited Adverse Event Reporting (CTEP-AERS)

Investigators are required by Federal Regulations to report serious adverse events as defined in the table below. Alliance investigators are required to notify the Investigational Drug Branch (IDB), the Alliance Central Protocol Operations Program, the Study Chair, and their Institutional Review Board if a patient has a reportable serious adverse event. CTCAE term (AE description) and grade: The descriptions and grading scales found in the revised NCI Common Terminology Criteria for Adverse Events (CTCAE) version 5.0 will be utilized for AE reporting beginning April 1, 2018. All appropriate treatment areas should have access to a copy of the CTCAE version 5.0. A copy of the CTCAE version 5.0 can be downloaded from the CTEP web site: [REDACTED] [REDACTED] All reactions determined to be “reportable” in an expedited manner must be reported using the Cancer Therapy Evaluation Program Adverse Event Reporting System (CTEP-AERS).

For further information on the NCI requirements for SAE reporting, please refer to the ‘NCI Guidelines for Investigators: Adverse Event Reporting Requirements’ document published by the NCI.

Note: All deaths on study require both routine and expedited reporting regardless of causality. Attribution to treatment or other cause should be provided.

9.4.1 Expedited Reporting Requirements for Adverse Events that Occur in a Non-IND/IDE trial ≤ 30 Days of the Last Administration

FDA REPORTING REQUIREMENTS FOR SERIOUS ADVERSE EVENTS (21 CFR Part 312)				
NOTE: Investigators MUST immediately report to the sponsor (NCI) ANY Serious Adverse Events, whether or not they are considered related to the investigational agent(s)/intervention (21 CFR 312.64)				
An adverse event is considered serious if it results in ANY of the following outcomes:				
1) Death 2) A life-threatening adverse event 3) An adverse event that results in inpatient hospitalization or prolongation of existing hospitalization for ≥ 24 hours 4) A persistent or significant incapacity or substantial disruption of the ability to conduct normal life functions 5) A congenital anomaly/birth defect. 6) Important Medical Events (IME) that may not result in death, be life threatening, or require hospitalization may be considered serious when, based upon medical judgment, they may jeopardize the patient or subject and may require medical or surgical intervention to prevent one of the outcomes listed in this definition. (FDA, 21 CFR 312.32; ICH E2A and ICH E6).				
ALL SERIOUS adverse events that meet the above criteria MUST be immediately reported to the NCI via CTEP-AERS within the timeframes detailed in the table below.				
Hospitalization	• Grade 1 Timeframes	• Grade 2 Timeframes	• Grade 3 Timeframes	Grade 4 & 5 Timeframes
Resulting in Hospitalization ≥ 24 hrs.	10 Calendar Days			24-Hour; 5 Calendar Days
Not resulting in Hospitalization ≥ 24 hrs.	Not required		10 Calendar Days	

NOTE: Protocol specific exceptions to expedited reporting of serious adverse events are found in the Specific Protocol Exceptions to Expedited Reporting detailed below.

Expedited AE reporting timelines are defined as:

- “24-Hour; 5 Calendar Days” - The AE must initially be reported via CTEP-AERS ≤ 24 hours of learning of the AE, followed by a complete expedited report ≤ 5 calendar days of the initial 24-hour report.
- “10 Calendar Days” - A complete expedited report on the AE must be submitted ≤ 10 calendar days of learning of the AE.

¹ Serious adverse events that occur more than 30 days after the last administration of investigational agent/intervention and have an attribution of possible, probable, or definite require reporting as follows:

Expedited 24-hour notification followed by complete report ≤ 5 calendar days for:

- All Grade 4, and Grade 5 AEs

Expedited 10 calendar day reports for:

- Grade 2 adverse events resulting in hospitalization or prolongation of hospitalization
- Grade 3 adverse events

- Expedited AE reporting timelines defined:
 - “24 hours; 5 calendar days” – The investigator must initially report the AE via CTEP-AERS ≤ 24 hours of learning of the event followed by a complete CTEP-AERS report ≤ 5 calendar days of the initial 24-hour report.
 - “10 calendar days” - A complete CTEP-AERS report on the AE must be submitted ≤ 10 calendar days of the investigator learning of the event.
- Any medical event equivalent to CTCAE grade 3, 4, or 5 that precipitates hospitalization (or prolongation of existing hospitalization) must be reported regardless of attribution and designation as expected or unexpected with the exception of any events identified as protocol-specific expedited adverse event reporting exclusions (see below).
- Any event that results in persistent or significant disabilities/incapacities, congenital anomalies, or birth defects must be reported via CTEP-AERS if the event occurs following treatment with an agent under a CTEP IND.
- Use the NCI protocol number and the protocol-specific patient ID provided during trial registration on all reports.

Additional Instructions or Exclusion to CTEP-AERS Expedited Reporting Requirements for Phase 2 and 3 Trials Utilizing an Agent Under a CTEP IND or non-CTEP IND:

- All adverse events reported via CTEP-AERS (i.e., serious adverse events) should also be forwarded to your local IRB.
- Adverse events attributed to chemotherapy need not be reported.
- Grade 1-3 nausea or vomiting and hospitalization resulting from such do not require AERS reporting, but should be reported via routine AE reporting.
- Grade 3 or 4 nausea or vomiting does not require AERS reporting, but should be reported via routine AE reporting.
- Grade 1-3 fatigue and hospitalization resulting from such do not require AERS reporting, but should be reported via routine AE reporting.
- Grade 3 or 4 fatigue does not require AERS reporting, but should be reported via routine AE reporting.

- Grade 1-3 radiation dermatitis and hospitalization resulting from such do not require AERS reporting, but should be reported via routine AE reporting.
- Grade 3 or 4 radiation dermatitis does not require AERS reporting, but should be reported via routine AE reporting
- Grade 1-3 lymphedema and hospitalization resulting from such do not require AERS reporting, but should be reported via routine AE reporting.
- Grade 3 lymphedema does not require AERS reporting, but should be reported via routine AE reporting
- Grade 1-3 pneumonitis and hospitalization resulting from such do not require AERS reporting, but should be reported via routine AE reporting.
- Grade 3 or 4 pneumonitis does not require AERS reporting, but should be reported via routine AE reporting
- Grade 2-3 acute coronary syndrome or myocardial infarction and hospitalization resulting from such do not require AERS reporting, but should be reported via routine AE reporting.
- Grade 3 or 4 acute coronary syndrome or myocardial infarction does not require AERS reporting, but should be reported via routine AE reporting
- Grade 1-3 chest pain and hospitalization resulting from such do not require AERS reporting, but should be reported via routine AE reporting.
- Grade 3 chest pain does not require AERS reporting, but should be reported via routine AE reporting
- Grade 2-3 wound infection and hospitalization resulting from such do not require AERS reporting, but should be reported via routine AE reporting.
- Grade 3 or 4 wound infection does not require AERS reporting, but should be reported via routine AE reporting
- Reporting of cases of secondary AML/MDS is to be done using the NCI/CTEP Secondary AML/MDS Report Form. New primary malignancies should be reported using Form Notice of New Primary.
- Death due to progressive disease should be reported as Grade 5 “Disease progression” in the system organ class (SOC) “General disorders and administration site conditions.” Evidence that the death was a manifestation of underlying disease (e.g., radiological changes suggesting tumor growth or progression: clinical deterioration associated with a disease process) should be submitted.
- All new malignancies must be reported via CTEP-AERS whether or not they are thought to be related to either previous or current treatment. All new malignancies should be reported, i.e. solid tumors (including non-melanoma skin malignancies), hematologic malignancies, myelodysplastic syndrome/acute myelogenous leukemia, and in situ tumors.

Secondary Malignancy:

A secondary malignancy is a cancer caused by treatment for a previous malignancy (e.g., treatment with investigational agent/intervention, radiation or chemotherapy). A secondary malignancy is not considered a metastasis of the initial neoplasm.

CTEP requires all secondary malignancies that occur following treatment with an agent under an NCI IND/IDE be reported via CTEP-AERS. Three options are available to describe the event:

- Leukemia secondary to oncology chemotherapy (e.g., acute myelocytic leukemia [AML])
- Myelodysplastic syndrome (MDS)
- Treatment-related secondary malignancy

Any malignancy possibly related to cancer treatment (including AML/MDS) should also be reported via the routine reporting mechanisms outlined in each protocol.

Second Malignancy:

A second malignancy is one unrelated to the treatment of a prior malignancy (and is NOT a metastasis from the initial malignancy). Second malignancies require ONLY routine reporting unless otherwise specified.

Whenever possible, the CTEP-AERS reports for new malignancies should include tumor pathology, history or prior tumors, prior treatment/current treatment including duration, any associated risk factors or evidence regarding how long the new malignancy may have been present, when and how the new malignancy was detected, molecular characterization or cytogenetics of the original tumor (if available) and of any new tumor, and new malignancy treatment and outcome, if available.

- CTCAE 4.0 grading listed where applicable.

Grade 4 toxicities that reflect life threatening events require CTEP-AERS reporting. Grade 4 wound healing per CTCAE can include wound healing that requires a major flap reconstruction. As this is part of breast reconstruction, this will not be recorded as a CTCAE complication. Grade 1-3 toxicity does not need CTEP-AERS reporting, but should be reported via routine AE reporting.

- CTEP-AERS reports should be submitted electronically.
- Pregnancy loss
 - Pregnancy loss is defined in CTCAE as “Death in utero.”
 - Any Pregnancy loss should be reported expeditiously, as Grade 4 “Pregnancy loss” under the Pregnancy, puerperium and perinatal conditions SOC.
 - A Pregnancy loss should NOT be reported as a Grade 5 event under the Pregnancy, puerperium and perinatal conditions SOC, as currently CTEPAERS recognizes this event as a patient death.
 - A neonatal death should be reported expeditiously as Grade 4, “Death neonatal” under the General disorders and administration SOC.
- When submitting CTEP-AERS reports for “Pregnancy”, “Pregnancy loss”, or “Neonatal loss”, the Pregnancy Information Form should be completed and submitted, along with any additional medical information (form is available on the CTEP website at [REDACTED]). The potential risk of exposure of the fetus to the investigational agent(s) or chemotherapy agent(s) should be documented in the “Description of Event” section of the CTEP-AERS report.

